5.3 Lifestyle restrictions

5.3.1 Meals and dietary restrictions

- Study participants will complete a light meal approximately 30 minutes prior to each morning dose of CBD/PSL administration and will complete a standard meal approximately 30 minutes prior to the evening dose. On days when PK assessments will be taken, study participants will complete a similar meal between periods.
- Study participants will complete assessments on the morning of Day 1 and Day 15 of Treatment Period 1 (Part B) and at Screening under fasting conditions.
- Study participants should keep their usual diet (besides the restrictions for the study) necessary for the maintenance of good health; excessive food consumption should be avoided.

- Padsevonil will be administered orally with 8oz (240mL) of water. Between 1 hour predose and 2 hours postdose, the total intake of beverages should be limited to 100mL. Water will be available ad libitum except for between 1 hour before and 2 hours after dosing.
- Study participants should refrain from consumption of grapefruit, starfruit, and pawpaw (as beverage, fruit or supplements) from 3 days before the start of study treatment until after the final dose.

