3.6.2 Part B

For all analyses (where applicable) the results will be presented by phase and treatment. For summary tables, results from Treatment Period 3 and 6 will be presented by CBD. Listings will also include phase day. Sequence in full will be used where applicable (defined in [Section 2.2.3](#)).

Phase, phase day, treatment (for listings and tables) and the corresponding treatment period and day from the protocol are defined in Table 3-3.

This document cannot be used to support any marketing authorization application and any extensions or variations thereof.

REDACTED COPY

Table 3–3: Definition of Phase - Part B

Protocol Treatment Period	Protocol Treatment Period Day	Phase	Phase Day	Treatment for Listings	Treatment for Tables
Screening	-28 to -2	Screening	-28 to -2	N/A	N/A
1	-1 to 2 (optional 15-16)	CBD Phase	-1 to 2 (optional 15-16)	CBD SD	CBD
Washout Period	-	CBD Phase	3 to 8 (or 17 to 22)	CBD SD	CBD
2	-1	PSL Phase	-1	CBD SD	CBD ^a
2	1 to 8	PSL Phase	1 to 8	PSL	PSL
Washout Period	-	PSL Phase	9 to 14	PSL	PSL
3	-1	Interaction Phase	-1	PSL	PSL ^b
3	1 to 16	Interaction Phase	1 to 16	CBD up-titration	CBD
4	1 to 7	Interaction Phase	17 to 23	CBD+PSL/CBD+Placebo	CBD+PSL/CBD+Placebo
CBD Dose Maintenance	-	Interaction Phase	24 to 27 ^c	CBD maintenance	CBD
5	1 to 7	Interaction Phase	28 to 34	CBD+PSL/CBD+Placebo	CBD+PSL/CBD+Placebo

Protocol Treatment Period	Protocol Treatment Period Day	Phase	Phase Day	Treatment for Listings	Treatment for Tables
6	1 to 7	Interaction Phase	35 to 41	CBD tapering	CBD
Follow-up	-	Follow-up	47 or 50	N/A	N/A

- = Day not specified in protocol; ^a If assessments are summarized by treatment, phase and day, then data will be presented as: PSL, PSL Phase, Day -1. If assessments are summarized by treatment, then data from Day -1 will attribute to CBD. ^b If assessments are summarized by treatment, phase and day, then data will be presented as: CBD, Interaction Phase, Day -1. If assessments are summarized by treatment, then data from Day -1 will attribute to PSL. ^c CBD dose maintenance will occur for at least 4 days. If dosing is maintained for more than 4 days, the phase day will need to be changed accordingly;

REDACTED COPY
 This document cannot be used to support any marketing authorization application or any extensions or variations thereof.

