9.1.1 Descriptive figures and summaries

The PK plasma concentrations and the PK parameters of PSL, CBD and metabolites will be summarized by phase, treatment and nominal sampling times using descriptive statistics (number of available observations [n], arithmetic mean, median, SD, minimum, maximum, geometric mean, geometric CV and 95% CI for the geometric mean [assuming lognormally distributed data]). Any samples that are obtained outside the tolerance window permitted at the specified time point will be discussed at the DEM and any possible exclusion from analysis will be documented accordingly. Values below the LLOQ will be reported with a clear sign (flag variable in the dataset) indicating that they were below the LLOQ. The plasma trough concentrations of PSL, CBD and metabolites will be summarized separately.

Individual participant concentration-time profiles of PSL and CBD by treatment (For Part A: PSL+Ethanol and PSL+Placebo, for Part B: CBD (single dose from Treatment Period 1), CBD+PSL and CBD+Placebo) will be displayed graphically in linear and semi-logarithmic scale.

Combined individual (spaghetti) plots will be displayed by treatment with all participants overlaid on the same plot (linear and semi-logarithmic scale).

Geometric mean profiles of plasma concentrations for PSL and CBD over time will be presented, with all treatments overlaid on the same plot, in both linear and semi-logarithmic scale. For the linear scale plot only, the lower and upper 95% confidence interval (CI) for the geometric mean will be displayed.

All plasma concentration figures will include the LLOQ on the semi-logarithmic scale plots and will be based on scheduled times.

Individual breath ethanol concentration-time data will be summarized by phase, treatment and nominal sampling times presenting the number of observations, geometric mean, lower and upper limit of the 95% CI for the geometric mean, geoCV(%), arithmetic mean, SD, median, minimum, and maximum. Individual participant breath ethanol concentration-time profiles will be displayed graphically in linear scale. Total ethanol dose will also be summarized by treatment.

The amount of urinary excretion of PSL (mg) per time interval after oral administration of PSL will be summarized by phase and treatment if measured.

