9.1.2 Statistical analysis of pharmacokinetics variables

The log-transformed PK parameters ($C_{\max,ss}$, AUC_{τ}) of PSL, CBD and metabolites, metabolite to parent ratio based on AUC_{τ} (for [Section 9.1.2.3](#) and [Section 9.1.2.4](#) only) and total ethanol dose will be analyzed separately by a mixed analysis of variance (ANOVA) with period, treatment and sequence as fixed effects and study participant by period and study participant as the random effects.

Due to the confounding of treatment within period within the design only the periods of interest will be included in any given comparison. For example, if the comparison is within the interaction phase then only Periods 4 and 5 will be kept in the model.

Period should be removed from the model statement due to confounding with treatment in any comparisons where either test or reference period only contains one treatment option. It will be left in the random statement as period is synonymous with treatment.

The PK parameter, t_{\max} , of PSL, CBD and metabolites will be analyzed separately with the non-parametric Hodges-Lehmann method to compute point estimates and associated 90% confidence intervals for the median of differences ((PSL+CBD) – CBD, and (PSL+CBD) – PSL).

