9.1.2.4 PSL interaction on CBD (Part B)

The log-transformed PK parameters ($C_{max,ss}$, AUC_{τ}) of CBD and its metabolite, and the metabolite to parent ratio based on AUC_{τ} (no transformation required) will be analyzed by the model specified in [Section 9.1.2](#), where period includes Treatment Periods 4 and 5 and treatment includes CBD+PSL and CBD+Placebo, to assess the effects of PSL on CBD.

Point estimates for the ratio of geometric means with and without PSL (CBD+PSL vs CBD+Placebo) and the respective 2-sided 90% CIs will be computed using the least squares means and the root mean squares of error from the mixed effects model, based on the log-transformed data with subsequent exponential transformation.

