10.1.2.2 CBD and PSL (Part B)

The similarity of the PD parameters between treatment will be analyzed using the model specified in [Section 10.1.2](#), where treatment includes CBD, PSL, CBD+PSL and CBD+Placebo.

The following contrasts will be calculated within the model:

- CBD+PSL (Treatment Period 4/5: Day 5) vs PSL (Treatment Period 2: Day 5) (primary comparison)
- CBD+PSL (Treatment Period 4/5: Day 5) vs CBD (Treatment Period 3: Day 16)
- CBD+PSL (Treatment Period 4/5: Day 5) vs CBD+Placebo (Treatment Period 4/5: Day 5)

This analysis will also be performed for PD variables measured in Treatment Period 4/5, Day 1. Any treatment effect may be compounded by time in the first and second comparison stated above. Additionally, there may be a learning effect due to study participants performing the PD assessments multiple times.

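### SAP 9.1.2 names the reference for the CBD tmax contrast as CBD, with no period or day, although the SAP's label for the randomised control is CBD+Placebo

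*SAP*

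**What the plan says.** The only inferential rule for tmax is in SAP 9.1.2. It asks for Hodges-Lehmann point estimates and 90% "confidence intervals for the median of differences ((PSL+CBD) – CBD, and (PSL+CBD) – PSL", applied separately to PSL, CBD and their metabolites. Neither reference carries a treatment period or day.

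Elsewhere the SAP treats CBD and CBD+Placebo as different things:

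- SAP 9.1.1, on the individual Part B profiles, lists "CBD (single dose from Treatment Period 1), CBD+PSL and CBD+Placebo".
- SAP 3.6.2 states: "For summary tables, results from Treatment Period 3 and 6 will be presented by CBD". Its Table 3-3 also gives the table label CBD to TP1 and to the maintenance days between TP4 and TP5. It labels TP4/5 as CBD+PSL or CBD+Placebo.
- SAP 10.1.2.2 describes a PD model "where treatment includes CBD, PSL, CBD+PSL and CBD+Placebo", and one of its contrasts is "CBD+PSL (Treatment Period 4/5: Day 5) vs CBD (Treatment Period 3: Day 16".

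For the other CBD parameters (Cmax,ss, AUCtau and the metabolite-to-parent ratio), SAP 9.1.2.4 sets the comparison explicitly: "where period includes Treatment Periods 4 and 5 and treatment includes CBD+PSL and CBD+Placebo, to assess the effects of PSL on CBD". It does not mention tmax.

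On feeding, Protocol 5.3.1 places a light meal about half an hour before each morning dose of CBD or PSL. The exception is TP1, which is done in the fasted state: "Study participants will complete assessments on the morning of Day 1 and Day 15 of Treatment Period 1 (Part B) and at Screening under fasting".

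**The concern.** A treatment label in an analysis rule is what a programmer selects on. Here the label given is not that of the randomised control, and it covers four other parts of Part B. If the data are selected on it, the comparison is no longer CBD with PSL against CBD with placebo under the same conditions. It becomes a comparison across periods that differ in feeding state, in single versus repeated dosing, and in calendar time. A shift in CBD tmax from any of those could then be read as an effect of PSL on the rate of CBD absorption. Participants without a TP1 profile would drop out of a paired analysis; Protocol Table 1-6 (note a) provides for participants who begin Part B in TP2.

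**Working it through.** The plan states no figure on this point, so there is nothing to reproduce. The check has three steps.

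**Step 1. Which periods can supply a CBD tmax?** A tmax needs serial samples after the dose. Labels are from the table-label column of SAP Table 3-3, sampling from the protocol schedules.

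| Period | SAP table label | CBD sampling | CBD tmax possible? |
|---|---|---|---|
| TP1, single dose, fasted | CBD | Serial, 0 to 24 h (Table 1-5, note o) | Yes |
| TP3, up-titration | CBD | Troughs only (Table 1-7, note c) | No |
| Maintenance days | CBD | None scheduled | No |
| TP4/5 Day 5, CBD steady state, after a light meal | CBD+PSL or CBD+Placebo | Predose and 0.25 to 12 h (Table 1-8) | Yes |
| TP6, taper | CBD | Troughs only (Table 1-9, note b) | No |

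Of the four periods labelled CBD, only TP1 can yield a tmax. SAP 9 does derive a TP1 tmax for CBD, so such a value will exist under that label. If the optional Day 15 dose is given, it carries the same label, and a participant could then have two candidate reference values. For 7-hydroxy-CBD the position differs: SAP 9 lists the TP1 parameters for the single dose of CBD only, and lists the metabolite's tmax beside Cmax,ss and AUCtau. No TP1 reference is planned for it.

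**Step 2. What would each contrast estimate?** Let d be the effect of PSL on CBD tmax. Let s be the combined shift from fasted single dosing in TP1 to fed steady-state dosing in TP4/5, including calendar order. Treating the shifts as additive:

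- CBD+PSL (TP4/5) minus CBD (TP1) estimates d + s.
- CBD+PSL (TP4/5) minus CBD+Placebo (TP4/5) estimates d. Both sides are fed and at CBD steady state, and the order is randomised.

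With d = 0 and assumed shifts s = 0, 0.5, 1 and 2 h, the first gives 0, 0.5, 1 and 2 h and the second gives 0 h throughout. This is an identity: it shows that s passes through in full, not how large s is. The documents give no value for s.

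**Step 3. How many pairs?** Part B plans 22 evaluable participants. TP1 needs 16 evaluable (Protocol 1.1.6), at least 16 according to Protocol 4.2.2. Protocol 9.10 allows up to 20 to be selected so that 16 complete; I take that sentence to refer to the TP1 cohort. Assuming a paired analysis, that all TP1 participants go on to TP4/5, and equal variability of the differences:

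| Pairs n | Loss, (22 − n)/22 | Walsh averages, n(n+1)/2 | Relative CI width, √(22/n) |
|---|---|---|---|
| 22 | 0% | 253 | 1.00 |
| 20 | 2/22 = 9% | 210 | 1.05 |
| 16 | 6/22 = 27% | 136 | 1.17 |

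The loss of precision is modest. The change in what is being compared matters more.

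**The case against.** The strongest reply is that nobody would read the sentence as pointing to TP1.

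- The sentence mentions neither TP1 nor a single dose nor fasting. Where the SAP means TP1 it says so, as in 9.1.1.
- It writes PSL+CBD where the defined label is CBD+PSL, so it is not using the labels strictly.
- SAP 2.1.2 puts this tmax under the steady-state interaction objective and gives single-dose CBD its own objective. SAP 2.2.3 states the aim as CBD kinetics with and without PSL.
- The only comparison that either document defines for the effect of PSL on CBD kinetics (Protocol 9.5.4, SAP 9.1.2.4) uses the placebo control of TP4/5.
- Leaving out the word placebo has a precedent: Protocol 9.4.1 lists PSL with ethanol placebo as an arm and then calls it PSL alone.
- The missing TP1 value for 7-hydroxy-CBD also makes TP1 an unlikely intention.

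All of this stands as evidence of intent. A reader might infer from the labels that the SAP plans to set fed steady-state dosing against the fasted single dose. The documents do not support that, because TP1 is reached only by matching labels and eliminating periods without profiles.

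The reply does not supply the missing specification. SAP 9.1.2.4 does not extend to tmax. The rule in 9.1.2 about keeping only the periods of interest is written for the ANOVA model, not for the Hodges-Lehmann analysis. The other reference in the same sentence, PSL, does agree with its Table 3-3 label, so reading CBD by its label is not perverse.

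**Conclusion.** The point holds as a wrongly named comparator in an operative analysis rule. CBD+Placebo was very probably intended, but the label written belongs to other periods, and the only one of those with a profile would give a non-randomised, confounded comparison.

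The consequence is limited. SAP 2.1.2 and 9 class tmax as an Other variable, no acceptance range or decision rule is attached to it, and the references for Cmax,ss and AUCtau are correctly stated in SAP 9.1.2.3 and 9.1.2.4. It would also be too strong to say that the reported CBD tmax result will be biased: that requires the analysis to follow the label against the stated objective, and requires food, repeated dosing or period to shift CBD tmax, a shift for which the documents give no figure. The range of 16 to 20 pairs rests on the assumptions in step 3 and is before dropout. The point is worth correcting because the correction is so cheap.

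**What to change.** In SAP 9.1.2, state the tmax contrast for CBD and 7-hydroxy-CBD as (CBD+PSL, TP4/5 Day 5) minus (CBD+Placebo, TP4/5 Day 5). This matches SAP 9.1.2.4.

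As an optional clarification, state the contrast for PSL and its metabolites as (CBD+PSL, TP4/5 Day 5) minus (PSL, TP2 Day 5). This is not strictly needed, since TP2 is the only period of Part B in which PSL is given alone.

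The cost is one line of text and no new data. SAP 1 requires a SAP amendment when an analysis definition is changed before database lock, so the line should go in by that route.

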9.1.2.1 Ethanol interaction on PSL (Part A)

The log-transformed PK parameters ($C_{\max,ss}$, AUC_{τ}) of PSL and its metabolites will be analyzed separately by a mixed ANOVA with period (Treatment Period 4 and 5) and treatment (PSL+Ethanol and PSL+Placebo) as fixed effects and study participant as the random effect to assess the effects of ethanol on PSL.

Point estimates for the ratio of geometric means with and without ethanol (PSL+Ethanol vs PSL+Placebo) and the respective 2-sided 90% CIs will be computed using the least squares means and the root mean squares of error from the mixed effects model, based on the log-transformed data with subsequent exponential transformation.

Lack of ethanol effect on PSL will be concluded if the 90% CI of the ratio between PSL+Ethanol and PSL+Placebo of the least squares means for the log transformed AUC_{τ} , and $C_{\max,ss}$ is within the conventional acceptance range of 80% to 125%.

9.1.2.2 PSL interaction on ethanol (Part A)

The individual metabolizing capacity will be characterized by calculating the total ethanol dose, i.e. the total amount of ethanol infused during Treatment Period 1/2 and Treatment Period 4/5.

Total ethanol dose will be analyzed by the model specified in [Section 9.1.2](#), where period includes Treatment Periods 1 or 2 and 4 or 5, and treatment includes PSL+Ethanol and Ethanol, to assess potential differences of metabolizing capacity between treatments. The ratio of the least squares means with and without PSL (PSL+Ethanol vs Ethanol), and its 90% CI will be calculated.

9.1.2.3 CBD interaction on PSL (Part B)

The log-transformed PK parameters ($C_{\max,ss}$, AUC_{τ}) of PSL and its metabolites, and the metabolite to parent ratio based on AUC_{τ} (no transformation required) will be analyzed

separately by a mixed ANOVA with treatment (PSL (Treatment Period 2) and CBD+PSL (Treatment Period 4/5)) as a fixed effect and study participant as the random effect to assess the effects of CBD on PSL. The SAS code stated in [Section 9.1.2](#) will be used with period removed.

Point estimates for the ratio of geometric means with and without CBD (CBD+PSL vs PSL) and the respective 2-sided 90% CIs will be computed using the least squares means and the root mean squares of error from the mixed effects model, based on the log-transformed data with subsequent exponential transformation.

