3.9 Changes to protocol-defined analyses

- Due to changes in ClinPharm Standards, Enrolled Set has been changed to All Study Participants Set, Pharmacokinetic Per-Protocol Set has been changed to Pharmacokinetic Set and Pharmacodynamic Per-Protocol Set has been removed.
- For Part A and B, period has been removed from the mixed analysis of variance (ANOVA) in the cases where it is confounded with treatment for PK and PD.
- For Part B, analysis of metabolite to parent ratio based on AUC_{τ} has been included for completeness.
- For Part A and B baseline by time interactions have been added.
- The following parameters were intended but omitted from the protocol and are included for completeness:
 - For Part A, t_{max} and C_{trough} have been included as PK parameters for PSL and its metabolites
 - For Part A, $C_{max,ss}$ and AUC_{τ} have been included as PK parameters for PSL metabolites
 - For Part B, C_{trough} has been included as PK parameters for PSL and CBD
 - For Part B, C_{max} , AUC_{0-1} , AUC , t_{max} , $t_{1/2}$ and CL/F have been included as PK parameters for the single dose of CBD within Treatment Period 1

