9 PHARMACOKINETICS

The calculation of the PK parameters of PSL and its metabolites (██████████), CBD and its metabolite (7-hydroxy-CBD) will be performed by the Quantitative Clinical Development Department, ICON PLC.

Pharmacokinetic concentrations and parameters will be summarized by phase and treatment using the PKS. Figures of summaries will be based on the PKS and figures of individual concentrations will be based on the FAS.

Pharmacokinetic parameters of PSL, CBD and metabolites will be calculated using the actual blood sampling times. $C_{\max,ss}$ and t_{\max} will be determined from the observed concentration and time data. When two or more identical peak concentrations are observed, t_{\max} will be defined as the time of the first occurrence. $AUC\tau$ will be computed using the linear trapezoidal rule.

For Part A, the PK variables used for PSL and its metabolites are: $C_{\max,ss}$, $AUC\tau$, t_{\max} and C_{trough} ; and for ethanol, total ethanol dose will be used.

For Part B, the following PK variables used for PSL and CBD:

- Primary: $C_{\max,ss}$ and $AUC\tau$
- Secondary: CL_{ss}/F and $t_{1/2}$
- Other: t_{\max}

In addition, the other PK variables (for Part B) used are:

- C_{max} , AUC_{0-t} , AUC , t_{max} , $t_{1/2}$ and CL/F for the single dose of CBD (Treatment Period 1)
- $C_{max,ss}$, AUC_{τ} and t_{max} for PSL metabolites and CBD metabolite
- The metabolite to parent ratio (based on $C_{max,ss}$ and AUC_{τ}) obtained from the plasma concentration-time profiles for PSL metabolites and CBD active metabolite

Metabolite to parent ratios will be corrected for molecular weight. The molecular weight (MW) of: PSL is 432.8; metabolite [REDACTED] is [REDACTED]; metabolite [REDACTED] is [REDACTED]; CBD is 314 and 7-hydroxy-CBD is 330.

For both study parts, depending on the outcome of the PK analyses of PSL and its metabolites, urine samples for additional PK analyses will be collected for measurement of urine concentrations of PSL and its metabolites if needed.

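### The metabolite-to-parent ratio in Part B is modelled untransformed, but the only effect measure its SAP sections give is a geometric mean ratio from log-transformed data

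*SAP*

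**What the plan says.** Three parts of the SAP bear on how the ratio is analysed.

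- SAP 9.1.2 lists the log-transformed Cmax,ss and AUCτ, then the metabolite-to-parent ratio (for 9.1.2.3 and 9.1.2.4 only) and total ethanol dose, and states that these "will be analyzed separately by a mixed analysis of variance (ANOVA) with period, treatment and sequence as fixed effects". The sentence can be read as including the ratio among the log-transformed parameters or as excluding it.
- SAP 9.1.2.3 (effect of CBD on PSL) enters the ratio with the note "no transformation required) will be analyzed". SAP 9.1.2.4 (effect of PSL on CBD) repeats it: "no transformation required) will be analyzed by the model specified in" the common section.
- Each section then has one output paragraph. In 9.1.2.3 it begins "Point estimates for the ratio of geometric means with and without CBD (CBD+PSL vs PSL) and the respective 2-sided 90% CIs will be computed". In 9.1.2.4 it begins "Point estimates for the ratio of geometric means with and without PSL (CBD+PSL vs CBD+Placebo) and the respective 2-sided 90% CIs will be computed". Both derive these from least squares means "based on the log-transformed data with subsequent exponential transformation".

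Two further statements matter. SAP 3.9 records the analysis as a change from the protocol ("For Part B, analysis of metabolite to parent ratio based on" AUCτ) without giving a scale or an effect measure. SAP 9 states: "Metabolite to parent ratios will be corrected for molecular weight".

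**The concern.** A treatment contrast from an untransformed model is a difference in arithmetic means. A ratio of geometric means comes from exponentiating a contrast on the log scale. The two sections name the first scale and the second output and give nothing to connect them.

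Other PK variables with special handling have their own output rule. SAP 9.1.2 assigns tmax a Hodges-Lehmann estimate with a 90% CI, and SAP 9.1.2.2 assigns total ethanol dose a ratio of least squares means with a 90% CI. The metabolite-to-parent ratio has none.

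At stake is whether the reported effect on this ratio can be interpreted and set beside the metabolite and parent AUCτ ratios from the same sections. Otherwise the programmer has to choose an effect measure, possibly after seeing data.

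**Working it through.** No power, sample size or significance figure in the documents depends on this analysis, so there is no stated figure to reproduce. The check is algebra with a supporting simulation.

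**Inputs.** From the documents: molecular weights of 314 (CBD) and 330 (7-hydroxy-CBD), SAP 9; 22 evaluable participants, CV 45% and correlation 0.5, SAP 2.3. The CV and correlation are stated for PSL AUCτ, and applying them to the metabolite-to-parent ratio is an assumption. Also assumed, because the documents do not give them: the level m of the ratio under the reference treatment (0.1 to 5), and a true treatment ratio g of 1.5.

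**Reading 1: the output paragraph applies to the untransformed ratio.**

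- Untransformed contrast: mg - m = m(g - 1).
- Exponentiated: exp(m(g - 1)), which depends on m.
- It equals g only when m = ln(g)/(g - 1). For g = 1.5 that is 0.4055/0.5 = 0.81.

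The simulation used 20,000 trials per level, with paired lognormal data, n = 22 and 90% CIs:

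| Assumed m | m(g - 1) | exp(m(g - 1)) | Simulated median | 90% CIs covering 1.5 |
|---|---|---|---|---|
| 0.1 | 0.05 | 1.05 | 1.06 | 0% |
| 0.5 | 0.25 | 1.28 | 1.31 | 42% |
| 1 | 0.50 | 1.65 | 1.72 | 77% |
| 2 | 1.00 | 2.72 | 2.97 | 20% |
| 5 | 2.50 | 12.18 | 15.2 | 4% |

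The simulated medians exceed the algebraic values because the simulation sets m as a geometric mean. At CV 45% the arithmetic mean is larger by a factor of sqrt(1 + 0.45²) = 1.097.

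The molecular weight correction for the CBD pair multiplies the ratio by 314/330 = 0.952. At m = 2 this moves the result from exp(1.00) = 2.72 to exp(0.952) = 2.59. A true treatment ratio would not move, because the constant cancels.

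**Reading 2: the output paragraph covers only Cmax,ss and AUCτ.** The visible text then defines no estimate or CI for the metabolite-to-parent ratio. The ordinary output would be the difference m(g - 1), which for the same 1.5-fold change runs from 0.05 to 2.50 over the levels above. It also scales with the molecular weight constant and is not comparable with the log-scale AUCτ ratios. A ratio of arithmetic least squares means would avoid the dependence on level, since mg/m = g, but the SAP states that rule only for ethanol dose.

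**Log scale.** The contrast is ln(mg) - ln(m) = ln(g), so exponentiating returns g at every m. In the same simulation the median was 1.50, the median 90% CI was about 1.28 to 1.75, and coverage was about 90% at all five levels. Moreover, log(ratio) = log(metabolite AUCτ) - log(parent AUCτ) + constant. With complete data from the same participants, the geometric mean ratio for this variable is therefore the metabolite geometric mean ratio divided by the parent one.

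**The case against.** The strongest reply is that the text never instructs anyone to exponentiate an untransformed difference. The note separates the metabolite-to-parent ratio from the log-transformed parameters, and the output paragraph confines itself to log-transformed data, so reading 2 is arguably the more natural. This stands. A reader might infer from the table that the trial would report a wrong ratio. The documents do not support that as a certainty, because the figures hold only under reading 1.

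Four further replies have weight:

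- SAP 9.1.2.3 refers to SAS code in 9.1.2 that is absent from the text available for review. It may request particular estimates for this variable, so a claim that none is defined anywhere would go too far.
- Untransformed analysis is not invalid. A difference in least squares means with its CI would be coherent if the SAP stated it.
- Little information is lost. Metabolite and parent AUCτ are both analysed on the log scale, and with complete data their quotient gives the point estimate, leaving only the CI missing.
- A reader might infer that the SAP introduced this endpoint to test a mechanism. The protocol's objectives table already lists it under Other for Part B. SAP 3.9 adds only its statistical analysis, and gives completeness as the reason.

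None of this removes the mismatch. Under either reading, the visible text does not give this variable a scale and an effect measure that belong together.

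**Conclusion.** The point holds as an internal inconsistency of minor severity. Under reading 1 the reported quantity is not a ratio. For an assumed 1.5-fold change it runs from 1.05 to 12.2 as the assumed reference level runs from 0.1 to 5. Under reading 2 the effect measure is unstated in the visible text, and a difference would still depend on the reference level.

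The dependence on level is algebraic. The particular figures rest on the assumed levels and treatment ratio, and the coverage figures also on the borrowed CV and correlation.

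A reader might infer that the Part B conclusions are at risk. They are not. The ratio has no acceptance range or decision rule, and the primary Cmax,ss and AUCτ analyses and the sample size do not use it.

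Logging is preferable to the stated scale. It fits the output paragraph already written, the lognormal assumption in SAP 9.1.1, and the log-scale AUCτ analyses alongside.

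**What to change.** In SAP 9.1.2.3 and 9.1.2.4, replace the bracketed note that no transformation is needed with a statement that the ratio is log-transformed. In 9.1.2, reword the list so that the metabolite-to-parent ratio is clearly among the log-transformed variables. The existing output paragraphs then cover it unchanged, giving a geometric mean ratio with a 90% CI.

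If the sponsor prefers to keep the untransformed scale, the alternative is to name the effect measure and its CI in both sections, for example a difference in least squares means, and to exclude this variable explicitly from the exponentiated output.

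The cost is a few words in three places. SAP 1 requires a SAP amendment when analysis definitions change before database lock, so the edit is small but formal. It needs no new data and no change to the sample size.
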